7.3. Lost to Follow-Up

A participant will be considered lost to follow-up if the participant repeatedly fails to return for scheduled visits and is unable to be contacted by the study site.

The following actions must be taken if a participant fails to attend a required study visit:

- The site must attempt to contact the participant and reschedule the missed visit as soon as possible. Counsel the participant on the importance of maintaining the assigned visit schedule, and ascertain whether the participant wishes to and/or should continue in the study;

- Before a participant is deemed lost to follow-up, the investigator or designee must make every effort to regain contact with the participant (where possible, 3 telephone calls and, if necessary, a certified letter to the participant's last known mailing address or local equivalent methods). These contact attempts should be documented in the participant's medical record;
- Should the participant continue to be unreachable, the participant will be considered to have withdrawn from the study.

8. STUDY ASSESSMENTS AND PROCEDURES

8.1. Administrative Procedures

The investigator (or an appropriate delegate at the investigator site) must obtain a signed and dated ICD before performing any study-specific procedures.

The age of each participant will be collected to critically evaluate the immune response and safety profile.

Study procedures and their timing are summarized in the [SoA](#). Protocol waivers or exemptions are not allowed.

Adherence to the study design requirements, including those specified in the [SoA](#), is essential and required for study conduct.

All screening evaluations must be completed and reviewed to confirm that potential participants meet all eligibility criteria. The investigator will maintain a screening log to record details of all participants screened and to confirm eligibility or record reasons for screening failure, as applicable.

Every effort should be made to ensure that protocol-required tests and procedures are completed as described. However, it is anticipated that from time to time there may be circumstances outside the control of the investigator that make it unfeasible to perform the test. In these cases, the investigator must take all steps necessary to ensure the safety and well-being of the participant. When a protocol-required test cannot be performed, the investigator will document the reason for the missed test and any corrective and preventive actions that they have taken to ensure that required processes are adhered to as soon as possible. The study team must be informed of these incidents in a timely manner.

For samples being collected and shipped, detailed collection, processing, storage, and shipment instructions and contact information will be provided to the investigator site prior to initiation of the study.

8.1.1. Telehealth Visits

Telehealth visits may be used to assess participant safety and collect data points. Telehealth includes the exchange of healthcare information and services via telecommunication technologies (eg, audio, video, videoconferencing software) remotely, allowing the participant and the investigator to communicate on aspects of clinical care, including medical advice, reminders, education, and safety monitoring. Assessments that may be performed during a telehealth visit are described in the [SoA](#).

Study participants must be reminded to promptly notify site staff about any change in their health status.

8.2. Efficacy and/or Immunogenicity Assessments

8.2.1. Blood Collection

Blood samples (approximately 20 mL per sample) will be collected from participants for immunogenicity testing as specified in the [SoA](#). Blood samples will be collected from all participants at Visit 1 (prior to study vaccination) and Visit 3 (1 month after study vaccination) for antibody assessment. The total blood sampling volume for individual participants is approximately 40 mL.

Blood samples will be processed at the study site, where the serum will be extracted, frozen, and stored. The serum samples will then be shipped to the central laboratory for analysis.

Instructions for the collection and handling of blood and serum samples will be provided in the laboratory manual. The date and time of each sample will be recorded. The immunogenicity serum samples must be processed and shipped as indicated in the instructions provided to the investigator site to maintain sample integrity. Any deviations from the immunogenicity sample handling procedure (eg, sample collection and processing steps, interim storage, or shipping conditions), including any actions taken, must be documented and reported to the sponsor. On a case-by-case basis, the sponsor may make a determination as to whether sample integrity has been compromised.

8.2.2. RSV Vaccine Antibody Testing

RSV A– and RSV B–neutralizing antibody titers will be measured at each blood sampling time point.

Sample collection may be halted or discontinued upon notification by Pfizer. This includes discontinuing sampling in dosed participants who are no longer eligible for the study as well as discontinuation for groups of participants or all participants.

All serum sample assays will be performed by Pfizer and/or at a facility designated by Pfizer.

8.2.3. Biological Samples

Serum samples will be used only for scientific research. Each sample will be labeled with a code so that the laboratory analyst testing the samples will not know the participant's identity, study visit, or study cohort associated with the sample. Samples that remain after performing assays outlined in the protocol may be stored by Pfizer. Unless a time limitation is required by local regulations or ethical requirements, the samples will be stored for up to 15 years after the end of the study and then destroyed. If allowed by the ICD, stored samples may be used for additional testing to better understand the immune responses to the vaccine(s) under study in this protocol, to inform the development of other vaccines or vaccine-related products, and/or for vaccine-related assay work supporting vaccine programs.

No testing of the participant's DNA will be performed.

The participant may request that their samples, if still identifiable, be destroyed at any time; however, any data already collected from those samples will still be used for this research. The biological samples may be shared with other researchers as long as confidentiality is maintained and no testing of the participant's DNA is performed.

8.3. Safety Assessments

Planned time points for all safety assessments are provided in the [SoA](#). Unscheduled safety measurements may be obtained at any time during the study to assess any perceived safety issues.

A clinical assessment, including a physical examination and medical history, will be performed on all participants at their first visit to establish a baseline. Significant medical history and any clinically significant observations from any physical examination will be documented in the CRF.

AEs, SAEs, NDCMCs, and AESIs will be collected, recorded, and reported as defined in [Section 8.4](#).

Participants will be observed for at least 30 minutes after vaccination and any acute reactions occurring during the first 30 minutes after administration of the study intervention will be recorded on the CRF.

Safety parameters also include reactogenicity e-diary reports of local reactions and systemic events (including fever) that occur in the 7 days after administration of the study intervention. These prospectively self-collected occurrences of local reactions and systemic events are graded as described in [Table 5](#), [Table 6](#), and [Table 7](#).

Unscheduled safety measurements may be obtained at any time during the study to assess any perceived safety issues.

8.3.1. Physical Examinations

A clinical assessment and physical examination will be performed at Visit 1, Visit 3, and unscheduled reactogenicity visits.

A physical examination should include vital signs (oral or tympanic or temporal artery temperature, heart rate, respiratory rate, and seated BP) and evaluation of any clinically significant abnormalities within the following body systems: general appearance; skin; head, eyes, ears, nose, and throat; heart; lungs; abdomen; musculoskeletal; extremities; and lymph nodes.

Investigators should pay special attention to clinical signs related to previous serious illnesses.

Physical examination findings collected during the study will be considered source record and will not be required to be reported, unless otherwise noted. Any untoward physical examination findings that are identified during the active collection period and meet the definition of an AE or SAE ([Appendix 2](#)) must be reported according to the processes in [Sections 8.4.1](#) to [8.4.3](#).

8.3.2. Vital Signs

Any untoward vital sign findings that are identified during the active collection period and meet the definition of an AE or SAE ([Appendix 2](#)) must be reported according to the processes in [Sections 8.4.1](#) to [8.4.3](#).

8.3.3. Clinical Safety Laboratory Assessments

Clinical safety laboratory assessments will not be collected in this study.

8.3.4. Electronic Diary for Reactogenicity

Participants will be required to complete a reactogenicity e-diary through an application installed on a provisioned device or on the personal device of the participant. They will be asked to monitor and record prespecified local reactions, systemic events, and temperature daily for 7 days or longer following vaccination, where Day 1 is the day of vaccination. Participants will receive reminders to complete the reactogenicity e-diary on a daily basis, starting on the day of study intervention administration (Day 1) through Day 7, or longer if there are ongoing symptoms.

The e-diary allows recording of these assessments each day, thus providing an accurate representation of the participant's experience.

Data on local reactions, systemic events, and temperature recorded in the e-diary will be transferred electronically to the e-diary vendor, where they will be available for review by investigators, their qualified designees, and sponsor staff at all times via an internet-based portal. At intervals agreed to by the vendor and Pfizer, these data will be transferred

electronically to Pfizer for analysis and reporting. These data do not need to be recorded by the investigator in the CRF, except for the following conditions:

- Grade 4 local reactions will be collected in the CRF.
- Any local reactions or systemic events occurring within the first 30 minutes after study vaccination must be recorded on the CRF. The time of onset (relative to vaccination) must be recorded.
- If a participant withdraws because of prespecified event(s) recorded in the e-diary, the event(s) should be recorded on the CRF, regardless of whether the investigator considers the event(s) to be clinically significant.
- The investigator or designee must obtain stop dates for any symptoms ongoing on the last day, from Day 7 onwards until resolution. The stop dates should be documented in the source documents and the information entered in the CRF.

Investigators (or appropriately qualified designees) are required to review the e-diary data online at frequent intervals to evaluate participant compliance and as part of the ongoing safety review.

All provisioned e-diary devices must be collected per the study [SoA](#).

8.3.4.1. Grading Scales

The grading scales used in this study to assess local reactions and systemic events as described below are derived from the FDA CBER guidelines on toxicity grading scales for healthy adult volunteers enrolled in preventive vaccine clinical trials.³⁵

8.3.4.2. Local Reactions

Following vaccination (where Day 1 is the day of vaccination), participants will be asked to assess redness, swelling, and pain at the injection site, and to record the symptoms in the e-diary or appropriate device daily.

Redness and swelling will be measured by the participant and recorded in measuring device units (range: 1 to 21; an entry in the e-diary of 21 will be denoted as ≥ 21), and then categorized during analysis as absent, mild, moderate, or severe based on the grading scale in [Table 5](#). Measuring device units can be converted to centimeters according to the following scale: 1 measuring device unit = 0.5 cm. Pain at the injection site will be assessed by the participant as absent, mild, moderate, or severe according to the grading scale in [Table 5](#).

If a severe (Grade 3) local reaction is reported in the reactogenicity e-diary, a telephone contact should occur to ascertain further details and determine whether a site visit is clinically indicated.

Only an investigator or a qualified designee is able to classify a participant's local reaction as Grade 4, after clinical evaluation of the participant, documentation from another medically qualified source (eg, emergency room or hospital record), or telephone contact with the participant. If a participant experiences a Grade 4 local reaction, the investigator must immediately notify the sponsor. A Grade 4 local reaction will be collected on the CRF.

If a local reaction persists beyond the end of the 7-day e-diary collection period, the participant will be requested to report that information and/or any new events that develop to the investigator or the study staff. The investigator will enter this additional information in the participant's source notes and CRF.

Table 5. Grading Scale for Local Reactions

	Mild (Grade 1)	Moderate (Grade 2)	Severe (Grade 3)	Grade 4^a
Redness	>2.0 cm to 5.0 cm (5 to 10 measuring device units)	>5.0 cm to 10.0 cm (11 to 20 measuring device units)	>10 cm Necrosis or exfoliative dermatitis	Necrosis or exfoliative dermatitis
Swelling	>2.0 cm to 5.0 cm (5 to 10 measuring device units)	>5.0 cm to 10.0 cm (11 to 20 measuring device units)	>10 cm Necrosis	Necrosis
Pain (at the injection site)	Does not interfere with activity	Interferes with activity	Prevents daily activity	Emergency room visit or hospitalization for severe pain at the injection site

a. Only an investigator or qualified designee is able to classify a participant's local reaction as Grade 4, after clinical evaluation of the participant, documentation from another medically qualified source (eg, emergency room or hospital record), or telephone contact with the participant. Grade 4 local reactions will be collected on the CRF and assessed by the investigator or qualified designee.

8.3.4.3. Systemic Events

Following vaccination (where Day 1 is the day of vaccination), participants will be asked to assess fatigue, headache, vomiting, nausea, diarrhea, muscle pain, and joint pain, and to record the symptoms in the e-diary or appropriate device daily. The systemic symptoms will be assessed by the participant as absent, mild, moderate, or severe according to the grading scale in [Table 6](#).

If a severe (Grade 3) systemic event is reported in the reactogenicity e-diary, a telephone contact should occur to ascertain further details and determine whether a site visit is clinically indicated.

Only an investigator or qualified designee is able to classify a participant's systemic event as Grade 4, after clinical evaluation of the participant, documentation from another medically qualified source (eg, emergency room or hospital record), or telephone contact with the participant. If a participant experiences a Grade 4 systemic event, the investigator must immediately notify the sponsor. A Grade 4 systemic event will be collected on the CRF.

Further, if a systemic event persists beyond the end of the 7-day e-diary collection period, the participant will be requested to report that information and/or any new events that develop to the investigator or the study staff. The investigator will enter this additional information in the participant's source notes and CRF.

Table 6. Grading Scale for Systemic Events

	Mild (Grade 1)	Moderate (Grade 2)	Severe (Grade 3)	Grade 4^a
Fatigue (= tiredness in e-diaries)	Does not interfere with activity	Some interference with activity	Prevents daily routine activity	Emergency room visit or hospitalization for severe fatigue
Headache	Does not interfere with activity	Some interference with activity	Prevents daily routine activity	Emergency room visit or hospitalization for severe headache
Vomiting	1 to 2 times in 24 hours	>2 times in 24 hours	Requires IV hydration	Emergency room visit or hospitalization for severe vomiting
Nausea	Does not interfere with activity	Some interference with activity	Prevents daily routine activity	Emergency room visit or hospitalization for severe nausea
Diarrhea	2 to 3 loose stools in 24 hours	4 to 5 loose stools in 24 hours	6 or more loose stools in 24 hours	Emergency room visit or hospitalization for severe diarrhea
Muscle pain	Does not interfere with activity	Some interference with activity	Prevents daily routine activity	Emergency room visit or hospitalization for severe muscle pain
Joint pain	Does not interfere with activity	Some interference with activity	Prevents daily routine activity	Emergency room visit or hospitalization for severe joint pain

a. Only an investigator or qualified designee is able to classify a participant's systemic event as Grade 4, after clinical evaluation of the participant, documentation from another medically qualified source (eg, emergency room or hospital record), or telephone contact with the participant. Grade 4 systemic events will be collected on the CRF and assessed by the investigator or qualified designee.

8.3.4.4. Temperature and Fever Assessment

A digital thermometer will be given to the participant with instructions on how to measure oral temperature at home. Temperature will be collected daily for 7 days or longer following vaccination (where Day 1 is the day of vaccination).

Fever is defined as an oral temperature of $\geq 38.0^{\circ}\text{C}$. The highest temperature for each day will be recorded in the e-diary, where possible. Temperature will be measured and recorded to 1 decimal place.

In the event of a fever on the last day the diary was completed, temperature will be measured daily until the fever has resolved (1 day of temperature $< 38.0^{\circ}\text{C}$) in order to collect a stop date in the CRF.

If a fever of $> 38.9^{\circ}\text{C}$ is reported in the e-diary, a telephone contact should occur to ascertain further details and determine whether a site visit is clinically indicated.

Only an investigator or qualified designee is able to classify a participant's fever as Grade 4, after clinical evaluation of the participant, documentation from another medically qualified source (eg, emergency room or hospital record), or telephone contact with the participant. Grade 4 fevers will be collected on the CRF.

Table 7. Ranges for Fever

	Mild (Grade 1)	Moderate (Grade 2)	Severe (Grade 3)	Grade 4 ^a
Fever	$\geq 38.0^{\circ}\text{C}$ to 38.4°C	$> 38.4^{\circ}\text{C}$ to 38.9°C	$> 38.9^{\circ}\text{C}$ to 40.0°C	$> 40.0^{\circ}\text{C}$

a. Only an investigator or qualified designee is able to classify a participant's fever as Grade 4, after clinical evaluation of the participant, documentation from another medically qualified source (eg, emergency room or hospital record), or telephone contact with the participant. Grade 4 fevers will be collected on the CRF.

8.4. Adverse Events, Serious Adverse Events, and Other Safety Reporting

The definitions of an AE and an SAE can be found in [Appendix 2](#).

The definitions of device-related safety events (ADEs and SADEs) can be found in [Section 10.5](#). Device deficiencies are covered in [Section 8.4.9](#).

AEs may arise from symptoms or other complaints reported to the investigator by the participant (or, when appropriate, by a caregiver, surrogate, or the participant's legally authorized representative), or they may arise from clinical findings of the investigator or other healthcare providers (clinical signs, test results, etc).

The investigator and any qualified designees are responsible for detecting, documenting, and recording events that meet the definition of an AE or SAE and remain responsible to pursue and obtain adequate information both to determine the outcome and to assess whether the event meets the criteria for classification as an SAE or caused the participant to discontinue the study (see [Section 7.1](#)).

During the active collection period as described in Section 8.4.1 each participant will be questioned about the occurrence of AEs in a nonleading manner.

In addition, the investigator may be requested by Pfizer Safety to obtain specific follow-up information in an expedited fashion.

8.4.1. Time Period and Frequency for Collecting AE and SAE Information

The time period for actively eliciting and collecting AEs and SAEs (“active collection period”) for each participant begins from the time the participant provides informed consent, which is obtained before the participant’s participation in the study (ie, before undergoing any study-related procedure and/or receiving study intervention), through and including Visit 4. At Visit 4 (2-month follow-up), the participant will be contacted by telephone to inquire about SAEs, including hospitalizations, NDCMCs, and AESIs since Visit 3.

- Nonserious AEs will be collected from informed consent through 1 month following study intervention administration (Visit 3).
- SAEs, including hospitalizations, NDCMCs, and AESIs will be collected from informed consent through the last study visit (Visit 4).

Follow-up by the investigator continues throughout the active collection period and until the AE or SAE or its sequelae resolve or stabilize at a level acceptable to the investigator.

When a clinically important AE remains ongoing at the end of the active collection period, follow-up by the investigator continues until the AE or SAE or its sequelae resolve or stabilize at a level acceptable to the investigator and Pfizer concurs with that assessment.

For participants who are screen failures, the active collection period ends when screen failure status is determined.

If the participant withdraws from the study and also withdraws consent for the collection of future information, the active collection period ends when consent is withdrawn.

If a participant permanently discontinues or temporarily discontinues the study because of an AE or SAE, the AE or SAE must be recorded on the CRF and the SAE reported via PSSA or using the Vaccine SAE Report Form.

Investigators are not obligated to actively seek information on AEs or SAEs after the participant has concluded study participation. However, if the investigator learns of any SAE, including a death, at any time after a participant has concluded study participation, and they consider the event to be reasonably related to the study intervention, the investigator must promptly report the SAE to Pfizer using the Vaccine SAE Report Form or, if applicable, via PSSA.

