1.3. Schedule of Activities

The SoA table provides an overview of the protocol visits and procedures. Refer to the [STUDY ASSESSMENTS AND PROCEDURES](#) section of the protocol for detailed information on each procedure and assessment required for compliance with the protocol.

The investigator may schedule visits (unplanned visits) in addition to those listed in the SoA table in order to conduct evaluations or assessments required to protect the well-being of the participant.

Table 2. Schedule of Activities

Visit Number	Visit 1	Visit 2	Visit 3	Visit 4	Unscheduled Reactogenicity Visit	Notes
Visit Description	Day 1 Vaccination	1-Week Follow-Up	1-Month Follow-Up	2-Month Follow-Up	Safety Assessment	
Visit Window (Days)		7 to 13 Days After Vaccination	28 to 35 Days After Vaccination	56 to 70 Days After Vaccination	N/A	Day relative to study intervention administration (Day 1)
Type of Visit						 : Clinic visit,  : Phone visit
Obtain written informed consent	X					Written informed consent must be obtained prior to undergoing any study procedures.
Obtain the participant's study number using the IRT system	X					Participant must be present and consented prior to obtaining the study number.
Record demography	X					Birth date, sex, race, and ethnicity.
Record significant medical history	X					
Record current/former tobacco usage	X					

Table 2. Schedule of Activities

Visit Number	Visit 1	Visit 2	Visit 3	Visit 4	Unscheduled Reactogenicity Visit	Notes
Visit Description	Day 1 Vaccination	1-Week Follow-Up	1-Month Follow-Up	2-Month Follow-Up	Safety Assessment	
Visit Window (Days)		7 to 13 Days After Vaccination	28 to 35 Days After Vaccination	56 to 70 Days After Vaccination	N/A	Day relative to study intervention administration (Day 1)
Type of Visit						: Clinic visit, : Phone visit
Perform a clinical assessment and a physical examination	X		X		X	Includes measurement of temperature, heart rate, respiratory rate, and seated blood pressure. See Section 8.3.1 and Section 8.10.5 for further details.
Review prior vaccination history	X					Review vaccination history in source documents to verify eligibility and prohibited prior vaccinations. Record 28 days of vaccination history in the CRF. See Section 6.9 .
Record any new nonstudy vaccinations		X	X	X	X	See Section 6.9.3 .
Collect details of prohibited medications and treatments	X	X	X	X	X	See Section 6.9.1 .
Confirm eligibility	X					See Section 5 .

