8.10.2. Visit 2 (1-Week Follow-Up)

- Contact the participant by telephone.
- Review the participant's e-diary data and record the assessment in the CRF. Assess compliance, record any medically attended events (including hospitalizations), and collect stop dates of any symptoms ongoing on the last day of the e-diary collection period in the CRF. For symptoms still ongoing, continue to follow up until resolution and document and record stop dates in the CRF.
- Remind the participant to bring the e-diary to the next visit.
- Obtain details of any nonstudy vaccinations and prohibited medications and treatments as described in [Section 6.9.1](#).
- Record AE, NDCMCs, SAEs, and AESIs as described in [Section 8.4](#) and [Section 10.2](#).
- Remind participants to inform the study staff of any illnesses or medical events (eg, healthcare visits or hospitalization) that occur for the duration of the trial as described in [Section 8.3.4](#) and [Section 10.5](#).
- If appropriate, discuss contraceptive use as described in [Section 10.3.1](#).
- Complete the source documents.
- The investigator or an authorized designee completes the CRFs.

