8.10.4. Visit 4 (2-Month Follow-Up)

- Contact the participant by telephone.
- Obtain details of any nonstudy vaccinations and prohibited medications and treatments as described in [Section 6.9.1](#).
- Review ongoing reactogenicity e-diary symptoms reported as present on the last day of the e-diary collection period and obtain stop dates. Record stop dates in the CRF if required.
- Record SAEs, NDCMCs, and AESIs as described in [Section 8.4](#) and [Section 10.2](#).
- Complete the source documents.
- The investigator or an authorized designee completes the CRFs.

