3.1.2.2. Adverse Events and Serious Adverse Events

Standard algorithms for handling missing AE dates and missing AE severity levels will be applied as described in the Pfizer vaccine data standard rules. Completely missing AE start dates will not be imputed.

The following derivations (yes/no) will be included for each participant:

1. Any AE reported through 1 month after vaccination: If the AE started on the same day of vaccination, and the AE start time is before the vaccination time, then this AE will not be counted. Otherwise, if the AE start time is missing or after the vaccination time, the AE will be included.
2. Any related AE reported through 1 month after vaccination: This is similar to the above except only the related AE is included.
3. Any immediate AE (AE start time is within 30 minutes after vaccination) reported after vaccination: This includes only AEs that started on the same day of vaccination and with a nonmissing AE start time that is within 30 minutes after vaccination.
4. Any severe or life-threatening AE reported through 1 month after vaccination.
5. Any AE leading to study withdrawal after vaccination.
6. Any AE leading to death after vaccination.
7. Any SAE reported throughout the study.
8. Any NDCMC reported throughout the study.
9. Any AESI reported throughout the study.

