3.3. Other Safety Endpoint(s)

3.3.1. Adverse Events

AEs are classified into 1 of 3 tiers. Different analyses will be performed for different tiers (refer to [Section 6.3.1](#)).

- Tier 1 events: These are prespecified events of clinical importance and are maintained in a list in the product's safety review plan.

Guillain-Barré syndrome (from Day 1 through Day 43 after vaccination, where Day 1 is the vaccination day), atrial fibrillation (from Day 1 through the 1-month follow-up visit), and polyneuropathy (from Day 1 through Day 43 after vaccination, where Day 1 is the day of vaccination) have been identified as Tier 1 events for RSVpreF among the age group intended for this study. The RSV program Tier 1 list of MedDRA PTs is maintained by the safety risk lead in the CAETeLiSt and is referenced in the safety surveillance review plan for the program. The current list of Tier 1 events referenced by this study for RSVpreF should be confirmed to ensure that appropriate Tier 1 events will be used to produce final tables/graphs before conducting an analysis.

- Tier 2 events: These are events that are not Tier 1 but are “relatively common.” A MedDRA PT is defined as a Tier 2 event if at least 4 participants in at least 1 vaccine group report the event.
- Tier 3 events: These are events that are neither Tier 1 nor Tier 2 events.

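### If Visit 3 is never made up, no scheduled contact asks about nonserious AEs between the Visit 2 call and 1 month; separately, the Tier 1 atrial fibrillation window ends at a visit instead of on a fixed day

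*Protocol*

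**What the plan says.** - **Collection of nonserious AEs.** Protocol 8.4.1: "Nonserious AEs will be collected from informed consent through 1 month following study intervention administration (Visit 3"). No day number is given. In the Schedule of Activities (1.3) the AE row is marked at Visits 1, 2 and 3 and at unscheduled reactogenicity visits, but not at Visit 4.
- **Visit 2.** This telephone call takes place "7 to 13 Days After Vaccination", and 8.10.2 includes AEs: "Record AE, NDCMCs, SAEs, and AESIs as described in" the AE sections.
- **Visit 3.** The window is "28 to 35 Days After Vaccination".
- **Visit 4.** Under 8.4.1, "the participant will be contacted by telephone to inquire about SAEs, including hospitalizations, NDCMCs, and AESIs since Visit 3". Section 8.10.4 agrees: "Record SAEs, NDCMCs, and AESIs as described in" the same AE sections, with no mention of nonserious AEs.
- **Analysis.** SAP 3.1.2.2 derives a yes/no variable for each participant: "Any AE reported through 1 month after vaccination". It gives no day, no unknown category and no rule for a participant without Visit 3. SAP 4 and 6.1.3.1 apply it to the safety population, which is everyone vaccinated.
- **Tier 1 windows.** SAP 3.3.1 lists "atrial fibrillation (from Day 1 through the 1-month follow-up visit"). In the same sentence, Guillain-Barré syndrome and polyneuropathy both end on Day 43. Tier 1 events receive a between-group difference, its confidence interval and a p-value (SAP 6.3.1).
- **Atrial fibrillation as an AESI.** Protocol 8.4.8 lists it, and 8.4.1 collects AESIs up to Visit 4.

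**The concern.** The percentage of participants with an AE within 1 month is a primary safety estimand (Protocol Section 3; SAP 2.2.1.2.2). It can be read at face value only if every vaccinated participant was asked about that month. Someone who takes the Visit 2 call, never completes Visit 3 and then answers the Visit 4 call is in contact with the site, yet no scheduled question covers nonserious AEs in the second part of the month. A yes/no variable with no unknown category would most likely put that silence under no.

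The atrial fibrillation problem is different. The data exist, but the rule that selects them depends on when each person attended. An onset 33 days after vaccination counts for a participant seen on day 35 and not for one seen on day 28. With no Visit 3, the window has no end, and two programmers could produce different Tier 1 tables from the same data.

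**Working it through.** **Nearest stated figure.** The plan gives no missed-visit rate and no expected AE rate. The closest figure is in Protocol 9.5: a non-evaluable rate of about 10%, leaving about 210 of 240 RSVpreF participants. 240 × 0.90 = 216, and the stated 210 implies 1 − 210/240 = 12.5%. This covers every reason for exclusion from the immunogenicity set, so it serves only as a rough ceiling for missed Visit 3.

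**Days without a scheduled enquiry.** Inputs are the Visit 2 window (days 7-13) and the first 28 days.
- Shortest gap: 28 − 13 = 15 days; 15/28 = 54%.
- Longest gap: 28 − 7 = 21 days; 21/28 = 75%.
- If Visit 3 would have fallen on day 35: 35 − 7 = 28 days; 28/35 = 80%.

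**Relative understatement.** Assume 2-5% never complete Visit 3, AEs arise at a constant rate, and none is reported spontaneously. Understatement ≈ share missing × share of the period not asked about.
- Low: 0.02 × 0.54 = 1.1%.
- High: 0.05 × 0.75 = 3.8%.

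**Absolute understatement.** Assume a 10% AE risk by day 28 with constant hazard, so F(d) = 1 − 0.90^(d/28). With m the share missing Visit 3, the observed rate is (1 − m) × F(Visit 3) + m × F(Visit 2), and the loss is m × [F(Visit 3) − F(Visit 2)].
- Visit 2 on day 13, Visit 3 on day 28: 0.1000 − 0.0477 = 0.0523 per person missed.
- Visit 2 on day 7, Visit 3 on day 35: 0.1234 − 0.0260 = 0.0974 per person missed.

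| Share missing Visit 3 (assumed) | Loss, percentage points | Participants, of 240 RSVpreF | Participants, of 120 placebo |
|---|---|---|---|
| 2% | 0.10 to 0.19 | 0.25 to 0.47 | 0.13 to 0.23 |
| 5% | 0.26 to 0.49 | 0.63 to 1.17 | 0.31 to 0.58 |
| 10% | 0.52 to 0.97 | 1.25 to 2.34 | 0.63 to 1.17 |

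Across assumed risks of 5-15% and missing shares of 1-10%, the loss runs from 0.03 to 1.4 points. For scale, the Clopper-Pearson 95% interval for 24/240 is 6.5% to 14.5%.

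**Atrial fibrillation window.** With Visit 3 in window, the Tier 1 period differs by 35 − 28 = 7 days between participants (35/28 = 1.25, a 25% spread). Day 43 for the other two events is 42 days after vaccination. That is before the Visit 4 window opens at day 56, so a fixed day of that kind is covered for anyone reached at Visit 4 in window.

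**Sections that pull apart.** The opening of 8.4.1 runs the active AE collection period through Visit 4, 8.4 has participants questioned about AEs during that period, and 8.4.1.2 has all nonserious AEs in it recorded. The later bullet of 8.4.1, the Schedule of Activities and 8.10.4 stop nonserious AEs at Visit 3.

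**The case against.** A reader might infer that anyone who misses Visit 3 is scored AE-free for time nobody asked about. The documents do not support that. Protocol 7.3 requires the site to make contact and reschedule, 8.1.1 allows telehealth for safety data, and 7.2.1 keeps participants who decline blood draws in safety follow-up. Participants are reminded to report illnesses, 8.4.1.2 puts spontaneous reports on the CRF, and AEs found at Visit 2 still count. A late Visit 3 can also supply the whole first month, because AE start dates are recorded and can be cut by onset. What stands is the narrower case of a Visit 3 that is never made up. Even there, counting the person as a no is inferred: SAP 3.1.2.1 writes an explicit default of no only for reactogenicity.

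A reader might also infer that atrial fibrillation goes unasked. It does not. It is an AESI, it is asked about at Visit 4, and AESIs over the whole study are summarised separately. Only the end of the Tier 1 window is at fault.

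The remaining objection is size. The trial is descriptive and blinded, the loss is under one point in every row of the table, and nothing shows that it would differ between arms. All of that stands, and it limits the point to an inexpensive repair.

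Finally, cutting the headline AE rate at 28 days looks tidy but costs more than it recovers. On the 10% assumption, risk rises from 10.0% at day 28 to 12.3% at day 35. Up to 2.3 points of properly elicited events would leave the rate, against about 0.5 points of loss at 5% missing.

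**Conclusion.** The point holds in limited form. For a participant whose Visit 3 is never made up, 54-75% of the first 28 days has no scheduled nonserious AE enquiry, and the derivation most likely treats that time as event-free. The understatement is about 1-4% relative, or 0.1-0.5 percentage points at a 10% AE risk, if 2-5% miss Visit 3. The missing rate, the AE risk and the constant hazard are all assumptions. No bias between arms is shown.

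The Tier 1 atrial fibrillation window needs no assumption: as written it differs by up to 7 days between participants seen in window, and it is undefined without Visit 3. This is a fault in the window's definition. It does not amount to missing data, and it is not evidence of an understated atrial fibrillation rate.

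**What to change.** 1. **Catch-up at Visit 4.** In the Schedule of Activities, 8.4.1 and 8.10.4, state that if Visit 3 was not done, the Visit 4 call also elicits nonserious AEs with onset within 1 month of vaccination. Start the Visit 4 look-back at the last completed contact instead of at Visit 3. Reconcile this with the parts of 8.4, 8.4.1 and 8.4.1.2 that run active AE collection through Visit 4.
2. **Fixed atrial fibrillation window.** In SAP 3.3.1, end the Tier 1 window on a stated day by onset date, as is done for Guillain-Barré syndrome and polyneuropathy. The data are already collected.
3. **Reporting.** Give the number without Visit 3 by arm, which also shows those not reached at Visit 4, whom step 1 cannot help. Add AEs with onset through 28 days after vaccination as a sensitivity summary, and leave the headline rate as it is.

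The cost is a footnote, a few sentences and two small summaries, with no added visit. The downside is recall: a call on days 56-70 about onsets between days 7 and 28 looks back 28 days (56 − 28) to 63 days (70 − 7), for the few participants concerned. SAP 5.3.1 already accepts recall to fill missed e-diary entries.
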